Protocol Title: Safety and Tolerability Study of Antimicrobial TheraGauze for Skin Abscess - Pilot Study

Phase of Study: I

Version date: 30March2017

Funding for this project is from the Department of Defense, through Soluble Systems, LLC

Principle Investigator: [name]  
Eastern Virginia Medical School  
[name]  
[name]  
[contact]  
[contact]  
[contact]  
Email: [[contact]](mailto:[contact])

Institutional Review Board: Eastern Virginia Medical School IRB (FWA00003956)

**Background.** Skin infections resulting in abscess, furunculosis, have become increasingly common in the past decade with the rapid emergence of community-associated methicillin-resistant *Staphylococcus aureus* (MRSA). The increasing incidence of these skin infections has stressed the medical system at the primary care, urgent and emergent care levels at significant cost. Methicillin-resistant *S. aureus* (MRSA) killed 18,650 Americans in 2005, exceeding the number of deaths attributable to HIV/AIDS (Klevens, Morrison et al. 2007). MRSA infections were identified for 368,600 hospital stays in the U.S. in 2005 for an estimated \$5 billion in hospitalization costs (Healthcare Cost and Utilization Project, DHHS).

The primary endpoint of the study is to evaluate the safety of and identify side effects of TheraGauze/tobramycin wound packing compared with standard of care management for cutaneous abscesses requiring incision and drainage. Current standard of care in most emergency and urgent care settings for community-acquired skin abscess is incision and drainage followed by packing with cotton wick ( $\pm$  iodoform) and anti-MRSA systemic antibiotics given orally for 5 – 7 days (Mistry, Weisz et al. , LoVecchio, Perera et al. 2009). Commonly prescribed oral antibiotic regimens include trimethoprim-sufamethoxazol, doxycycline, and clindamycin. Common side effects from these systemic antibiotics include diarrhea (~20%), nausea, and rash (Powell and Wenzel 2008). Uncommon but severe side effects include *C. difficile* colitis, Stevens-Johnson Syndrome, toxic epidermal necrolysis, hepatitis, and aplastic anemia (Bell, Foster et al. , Mistry, Schwab et al. 2009).

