#### Methods:

*Study Population:*

Subjects from the Hampton Roads region of southeastern Virginia will be recruited from the hospital emergency department site staffed by EVMS physicians at Sentara Norfolk General Hospital.

*Study Size:*

We anticipate screening 200 patients in order to enroll and randomize 100 subjects. Subjects will be randomized 2:1 to the TheraGauze+tobramycin or iodoform wick/ plain cotton wick, respectively. We anticipate 50 participants completing the study. The 50% retention rate is typical for emergency department populations.

*Subject Eligibility:*

Inclusion criteria:

- Ages  $\geq 18$  to  $\leq 65$  years at time of enrollment
- Subject has skin abscess (furuncle) requiring incision and drainage
- Erythema surrounding abscess
- Induration of  $\geq 2$ cm in maximal diameter
- Fluctuance or purulent head evident
- Tenderness at abscess
- No or mild fever  $\leq 38.5^{\circ}\text{C}$
- Male or female
- Ability to read and understand the English language at a level sufficient to provide informed consent and comply with study requirements
- Subject is willing and able to comply with all study requirements

Exclusion criteria:

- Systemic illness or deep-seated infection requiring inpatient admission (i.e. hypotension, tachycardia, or tachypnea)
- Deep seated infection requiring referral to surgery
- Subject requires intravenous antibiotics for suspicion of systemic spread of infection (i.e. suspicion of bacteremia)
- Extensive cellulitis extending  $> 6$ cm beyond the area of induration
- Fever  $> 38.5^{\circ}\text{C}$
- Allergy to any aminoglycoside antibiotic, sulfamethoxazole-trimethoprim, doxycycline, clindamycin.
- An underlying medical condition that impairs normal immune function (e.g. AIDS, cancer, diabetes, lupus, rheumatoid arthritis, organ or marrow transplantation, ulcerative colitis, Crohn's disease)
- Subject is pregnant or breastfeeding and/or a woman of childbearing potential who is not surgically sterile, not at least 2 years postmenopausal, or does not practice contraception methods, unless sexually abstinent for the duration of the study.
- Subject has any medical or psychiatric condition, in the opinion of the investigator, could jeopardize the subject's health or compromise the subject's ability to participate in the study.
- Subject has prior treatment with antibiotics in the preceding 7 (seven) days.

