    - Cleocin (clindamycin)

Phone Follow up Contact Day 2 (+2)

Return visit reminder and wound status follow up performed by Sentara Study Coordinator.

- Questions
  - Fever since leaving ED? (y/n, record temp if taken)
  - If prescribed, was antibiotic prescription filled (y/n)
  - If prescribed, has antibiotic been taken (y/n, # doses)
  - If antibiotics taken, were any side-effects noted (y/n, list)
  - Increased or decreased pain (y/n, increased/decreased)
  - Increased or decreased size of redness (y/n, increased/decreased)
  - Any new symptoms? (y/n, list) Specific questions will include: presence of rash, loose stool, nausea, vomiting, abdominal discomfort, headache, dizziness, drowsiness, thrush, as well as any change in local signs or symptoms including pain and redness, new skin lesions, enlarged lymph nodes, and sore or white spots in the mouth.

Visit 2 - Day 3 -1/+2: (ED)

Subjects' wound status will be evaluated. The following information will be collected and recorded on a hard copy Case Report Form at this visit:

- Questions about infection
  - Infection overall (better/same/worse)
  - Fever > 38°C at home since incision? (y/n)
  - Persistent discharge (y/n)
  - Pain (increased/same/decreased/resolved)
  - Medical evaluation between day 1 and day 3 visit (y/n)
  - New lesions (y/n)
  - Was an p.o. antibiotic prescribed (y/n)
    - If yes, was the prescription filled (y/n)
    - How many doses have been taken so far? (##)
  - Any diarrhea? (y/n)
  - Any nausea or vomiting? (y/n)
  - Any abdominal discomfort? (y/n)
  - Any new rash? (y/n)
  - Any other new symptoms including headache, dizziness, drowsiness, thrush, as well as any change in local symptoms.
  -
- Bacterial burden in wound bed – Wound culture performed using quantitative methods for culturing wound base (Gardner, Frantz et al. 2006). Cultures taken to [name] lab for quantitation, swab may be stored at 4°C, if obtained after business hours.
  - Quantitation of bacteria present (colony counts performed in [name] lab)
  - Speciation of bacteria present (CHKD clinical microbiology laboratory using CLSI standards)
  - Antibiotic susceptibility testing of bacteria present (CHKD clinical microbiology laboratory using CLSI standards)
- Wound assessment
  - Fever > 38°C in ED? (y/n, record temp)
  - Packing present (y/n)
  - Erythema at widest diameter (mm)

- Abscess induration at widest diameter (mm)
    - Tenderness around the wound? (y/n)
    - Removal of packing

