**ASSESSMENT OF SAFETY**

Subjects must be seen by a physician or an appropriately trained healthcare professional at every study visit, and the evaluation must be documented.

**Adverse Events.** An AE is any untoward medical occurrence in a clinical investigation subject administered a pharmaceutical product and which does not necessarily have to have a causal relationship with this treatment. An AE can therefore be any unfavorable and unintended sign (including an abnormal laboratory finding, for example), symptom, or disease temporally associated with the use of a medicinal product, whether or not considered related to the medicinal product.

**Causality Assessment.** For all AEs, the PI will provide an assessment of causal relationship to the study drug. Causal relationship must be assessed by answering the following question: Is there a reasonable possibility the study drug caused the event?

**Yes:** There is evidence to suggest a causal relationship between the study drug and AE, i.e.: there is a reasonable temporal relationship between the study drug and the event, and the event is unlikely to be attributed to underlying/concurrent disease, other drugs, or other factors.

**No:** There is no evidence to suggest a causal relationship between the study drug and AE, ie: there is no reasonable temporal relationship between the study drug and the event, or the subject did not take the study drug, or the event is likely to be attributed to underlying/concurrent disease, other drugs, or other factors, or the event is commonly occurring in the (study) population independent of drug exposure.

**Adverse Reaction.** An AE assessed as likely having a causal relationship with the intervention (i.e., TheraGauze/tobramycin). Specifically focusing on local-toxicity adverse reactions, we will evaluate for increasing redness, increasing pain or a new rash at the site of the packed wound. Increasing pain or redness could be due to progression of the infection (cellulitis/abscess) or local toxicity or reaction to the tobramycin in the TheraGauze/tobramycin packing. This will be assessed by an Investigator. Increasing purulent drainage or the identification of new areas of fluctuance requiring an additional incision and drainage procedure will be assessed as progression of the infection rather than evidence of local toxicity or reaction to the tobramycin.

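### Rash is recorded without its site, and pain without a Visit 1 value or comparison time, so local reactions cannot be reliably compared between arms

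*Combined protocol and SAP*

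**What the plan says.** The Adverse Reaction paragraph of Assessment of Safety sets out the local-toxicity signs: "we will evaluate for increasing redness, increasing pain or a new rash at the site of the packed wound". The primary endpoint is the safety and side effects of the packing compared with standard care.

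The items meant to capture these signs are listed under Study Treatments:

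- **Rash.** Visits 2 and 3 ask "Any new rash? (y/n"). Both phone scripts place rash in a general list: "Specific questions will include: presence of rash, loose stool, nausea, vomiting, abdominal discomfort".
- **Pain.** Visits 2 and 3 use "Pain (increased/same/decreased/resolved"). The calls ask whether pain has gone up or down. The Visit 1 list has no pain item. Tenderness at entry appears only as an inclusion criterion ("Tenderness at abscess").
- **Redness.** Erythema at its widest is measured in millimetres at Visits 1, 2 and 3.
- **Open prompts.** The calls add "as well as any change in local signs or symptoms including pain and redness". Visits 2 and 3 ask "Any other new symptoms including headache, dizziness, drowsiness, thrush, as well as any change in local symptoms".
- **Antibiotics.** Both calls ask those who took an antibiotic to list any side effects.

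Under Design, the TheraGauze arm starts without systemic antibiotics, and an oral antibiotic is optional in the control arm. The Background states: "Common side effects from these systemic antibiotics include diarrhea (~20%), nausea, and rash".

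**The concern.** Two of the three named signs are collected in a form that does not match their definition. The definition of rash depends on site, and the rash items carry none. The definition of pain depends on an increase, and the pain items do not say from when.

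What is at stake is the comparison between arms. Rash from oral antibiotics is expected mainly in controls, and rash from the packing only in the TheraGauze arm. If both go into one yes/no item, an excess of site reactions on TheraGauze can be offset by drug rash in controls. The Statistical Analysis Plan intends equivalence tests without naming the outcomes. If any-rash is one of them, such an offset would distort the interval being tested. Neither the site of a rash nor pain at Visit 1 can be restored at analysis if it was not written down.

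**Working it through.** The point concerns data capture, so the plan has no figure to reproduce.

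**1. Each sign against the listed items**

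| Sign | Visit 1 | Calls | Visit 2 | Visit 3 | What can be derived |
|---|---|---|---|---|---|
| Redness | mm | direction | mm | mm, plus a category | Change in mm |
| Pain | none | direction | category | category | The subject's own comparison, time unstated |
| Rash | none | presence | yes/no | yes/no | Occurrence, not site |

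**2. Pain.** Neighbouring items do state a reference. Fever is asked since leaving the ED (calls) or since incision (Visits 2 and 3), and new lesions at Visit 3 are asked since Day 3. Pain has no such anchor. Let pain be P0 before incision, P1 at the first call and P2 at Visit 2, with P1 < P2 < P0. The Visit 2 answer is then a decrease against P0 and an increase against P1, so the same subject does or does not show the sign according to an unstated choice. The tenderness item (yes/no) at Visits 2 and 3 does not settle this. Every eligible subject is tender at entry, so it can show resolution but not worsening from entry.

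**3. Rash: does another item supply the site?**

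- The open prompts invite local complaints but do not ask where a rash is. At the calls, the local prompt names pain and redness, while rash sits in the general list.
- The antibiotic side-effect list appears only at the calls and has no location.
- An adverse reaction is defined only for TheraGauze/tobramycin, and not having taken the study drug is one ground for a causality answer of No. Attribution therefore gives no matching count of local reactions to the control wick.
- The documents do not show an adverse event page, so whether one records site cannot be checked.

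**4. Illustration of the rash mixing.** All four rates are assumptions. The Background gives no rate for rash.

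- L = site-rash rate on TheraGauze: 5% or 10%
- r = rash rate among those taking an oral antibiotic: 3% to 10%
- s = share of controls given an antibiotic: 50% to 100%
- q = share of the TheraGauze arm given an antibiotic later: 0 or 10%
- The control wick is taken to cause no site rash, and the two kinds of rash are taken as independent.

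Any-rash risk on TheraGauze = 1 - (1 - L)(1 - q r). Any-rash risk in control = s r. The true site-rash difference is L. The recorded difference falls short of L by r[s - q(1 - L)], which is positive whenever s exceeds q(1 - L).

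- L = 5%, lowest (r = 10%, s = 100%, q = 0): 5.0 - 10.0 = -5.0 points.
- L = 5%, highest (r = 3%, s = 50%, q = 10%): 1 - 0.95 × 0.997 = 5.3%; 5.3 - 1.5 = +3.8 points.
- L = 10%, lowest (same inputs as the first line): 10.0 - 10.0 = 0 points.
- L = 10%, highest (same inputs as the second line): 1 - 0.90 × 0.997 = 10.3%; 10.3 - 1.5 = +8.8 points.

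Within the TheraGauze arm there is little mixing. With q = 0, no recorded rash there is antibiotic rash. With q = 10%, the antibiotic share runs from (10.27 - 10)/10.27 = 2.6% to (5.95 - 5)/5.95 = 16%.

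**5. Scale.** Study Size expects 50 completers at 2:1, so about 50 × 2/3 = 33 and 50/3 = 17 if retention is equal in the two arms. One antibiotic rash among 17 controls moves the control rate by 1/17 = 5.9 points.

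**The case against.** The strongest defence is that local toxicity is not read off a tick box. A trained professional sees the subject at every visit, an investigator decides whether increasing pain or redness is infection or reaction, and the PI judges causality for every adverse event with other drugs in mind. The open prompts solicit local complaints, the calls list antibiotic side effects separately, and later addition of an antibiotic is recorded. The TheraGauze arm starts without systemic antibiotics, so a rash there is nearly always free of this confusion. Comparing any rash between arms is also legitimate in itself, since avoiding systemic side effects is the stated main benefit.

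Most of this stands, and it rules out two stronger readings. A reader might infer that the forms cannot yield the local-toxicity signs at all. That is wrong for redness, which is measured in millimetres at every visit, and too strong for pain, which can be recorded as increased. A reader might also infer that reactions will be wrongly classified. The documents do not show that, because investigator judgement may pick up a site reaction from the open answers.

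What the defence does not supply is a count of site reactions collected in the same way in both arms. Nothing listed requires the site of a rash, and attribution is defined for one arm's product only.

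**Conclusion.** The point holds in a limited form, as a cheap improvement. Redness is adequately captured. For rash and pain, the listed items do not support a reliable between-arm tabulation of local reactions: site rash can be mixed with oral-antibiotic rash, mainly in controls or in TheraGauze subjects given an antibiotic later, and a pain change can be misclassified.

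The size is unknown. The range in the working depends wholly on assumed rates and shows only that the any-rash difference can understate the site-rash difference, by a little or by enough to reverse its sign. A reader might infer that the two kinds of rash cancel exactly. That happens only for particular input values, such as equal rates with every control treated, and nothing in the documents supports those values. The conclusion also assumes that no adverse event page outside the documents already requires site. If one does, the rash half of the point falls away.

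**What to change.** - At both calls and at Visits 2 and 3, in both arms, replace the single rash item with two yes/no items: new rash at or next to the packed wound, and new rash elsewhere. Tabulate only the first as a local sign. Any-rash can still be reported for overall tolerability.
- Record a pain rating at Visit 1, before incision and at discharge, and at each later contact.
- State the comparison time for the increase/decrease question, for example since the last contact.
- Use these data for descriptive comparison between arms. Set no numeric pain threshold that triggers clinical action, because local-toxicity reactions feed the Stopping Rules, and leave causality with the investigator as now.

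The cost is a small amendment to the forms and phone scripts, which become slightly longer.

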**Guidelines for Adverse Event Severity Assessments**

**Mild.** Minor awareness of signs or symptoms that are easily tolerated without specific medical intervention.

**Moderate.** Discomfort that interferes with usual activities and may require minimal intervention.

**Severe.** Significant signs or symptoms that are incapacitating with an inability to work or perform routine activities and/or that require medical intervention.

**Serious Adverse Events.** An SAE is any untoward medical occurrence that at any dose: is life threatening, requires in-patient hospitalization or prolongation of existing hospitalization, results in persistent or significant disability/incapacity. Important medical events may be considered serious when, based on appropriate medical judgment, they may jeopardize the subject and may require medical or surgical intervention to prevent one of the outcomes listed in this definition. If a serious and unexpected AE occurs for which there is evidence suggesting a causal relationship between the drug and the event the event must be reported as a serious and unexpected suspected adverse reaction. SAE will be reported to the local IRB and the FDA within 5 calendar days.

All unanticipated problems involving risk to subjects or others, serious adverse events related to participation in the study and subject deaths related to participation in the study should be promptly reported by [contact]), by email ([contact]), or by [contact]) to the USAMRMC, Office of Research Protections, Human Research Protection Office. A complete written report will follow the initial notification. In addition to the methods above, the complete report will be sent to the U.S. Army Medical Research and Materiel Command, ATTN: MCMR-ZB-PH, [name].

**Stopping Rules.** Adverse reactions, including local-toxicity adverse reactions, or SAEs will lead to immediate return to the SNGH ED for assessment and removal of the TheraGauze/tobramycin wound packing. The investigator will assess the need for treatment of the adverse reaction or SAE and, if necessary, either treat or refer for treatment, as appropriate. The subject will continue with their scheduled follow up: Day 3 visit in the ED, Day 6 phone follow up, and Day 7 visit in the CHKD Infectious Diseases Clinic

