#### **ROLES OF RESEARCH TEAM MEMBERS**

Physician investigators and Emergency Room staff will identify potential subjects and will notify the coordinator. The coordinator will explain the study and she or the physician will obtain informed consent. The physician will collect medical history culture the wound, and care for the wound per standard of care, using TheraGauze with tobramycin or standard gauze per randomization. The coordinators will ensure that all data are collected and recorded in the study chart, collect lab results, schedule follow-up appointments and make telephone contacts. Routine cultures and sensitivities will be performed in the hospital laboratories. The research lab staff will perform quantitative analysis. Coordinators and lab staff will enter data into the database. The statistician, with the PI, will analyze the results. The PI will oversee all of the above activities as well as performing most of the Visit 3 clinical assessments. and report findings to the sponsor.

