#### **RESEARCH MONITOR.**

All Serious Adverse Event (SAE) reports will be sent to the Research Monitor, [name], within 24 hours. The Research Monitor will also review subject charts for safety on a 3 to 6 month basis, assessing for evidence of tolerability or superiority/inferiority between the arms, and will discuss her findings with the PI. The Research Monitor may discuss the protocol with the investigators, interview subjects, and consult with others outside the study about the research. She shall have the authority to stop the protocol, remove subjects from the protocol, and take any necessary steps to protect the safety and well-being of subjects until the IRB can assess the Monitor's report. The Research Monitor shall have the responsibility to promptly report her observations and findings to the IRB or other designated official. The Research Monitor is required to review all unanticipated problems involving risks to subjects or others, serious adverse events and all subject deaths associated with the protocol and provide an unbiased written report of the event. At a minimum, the research monitor must comment on the outcomes of the event or problem and in the case of a serious adverse event or death, comment on the relationship to participation in the study. The research monitor must also indicate whether he/she concurs with the details of the report provided by the principal

investigator. Reports for events determined by either the investigator or research monitor to be possibly or definitely related to participation and report of events resulting in death must be promptly forwarded to the USAMRMC ORP HRPO.

Study Visit Schedule:

PROCEDURE	VISIT 1	VISIT 2	VISIT 3
	Screening/Day 1	Day 3-1/+2 days	Day 7±2 days
Consent	X		
Inclusion/exclusion	X		
Demographics	X		
Medical history	X		
History and current symptoms	X	X	X
Temperature, wound assessment	X	X	X
Culture abscess	X	X	
Randomization	X		
Apply wick	X		
Provide prescription if applicable	X		
Remove packing (if applicable)			
Follow-up phone call Day 2 (+2)	X		
Follow-up phone call day prior to Day 7 visit		X	

REFERENCES

Andrew, R., G. Luecke, S. Dozier and D. G. Diven (2012). "A pilot study to investigate the efficacy of tobramycin-dexamethasone ointment in promoting wound healing." *Dermatol Ther (Heidelb)* **2**(1): 12.

Bell, T. L., J. N. Foster and M. L. Townsend "Trimethoprim-sulfamethoxazole-induced hepatotoxicity in a pediatric patient." *Pharmacotherapy* **30**(5): 539.

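### An anticipated, non-serious TheraGauze reaction has no required route to the Research Monitor before her 3-to-6-month chart review, and the Stopping Rules act only on the affected subject

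*Combined protocol and SAP*

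**What the plan says.** The Stopping Rules paragraph, at the end of the Assessment of Safety material, states: "Adverse reactions, including local-toxicity adverse reactions, or SAEs will lead to immediate return to the SNGH ED for assessment and removal of the" packing. The investigator treats or refers as needed, and the subject keeps the remaining scheduled contacts. The paragraph gives no event count, no condition for pausing enrolment and no notice to the Research Monitor.

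Trial-level oversight is in the Research Monitor section:

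- Event by event: "All Serious Adverse Event (SAE) reports will be sent to the Research Monitor" within 24 hours. In addition, "The Research Monitor is required to review all unanticipated problems involving risks to subjects or others, serious adverse events and all subject deaths". No deadline is stated for unanticipated problems.
- Periodically: she will "review subject charts for safety on a 3 to 6 month basis, assessing for evidence of tolerability or superiority/inferiority between the arms".
- Authority: "She shall have the authority to stop the protocol, remove subjects from the protocol, and take any necessary steps". No trigger is attached to this power.

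The events at issue are defined under Adverse Reaction. For local toxicity, "we will evaluate for increasing redness, increasing pain or a new rash at the site of the packed wound". An adverse reaction is an AE judged likely to have been caused by the intervention. On who sees them: "For all AEs, the PI will provide an assessment of causal relationship to the study drug". The PI also rates the severity of each AE. Roles of Research Team Members adds: "The PI will oversee all of the above activities as well as performing most of the Visit 3 clinical assessments".

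**The concern.** Safety is the primary endpoint of this Phase I pilot, and local reactions to the packing are among the effects it sets out to find. A single case of more pain or redness is hard to read, because the protocol itself accepts that these signs may come from the infection or from the tobramycin. Several cases viewed together tell more than each one alone. The person with stated authority to stop the protocol is not required to see them as they accumulate.

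The gap is not confined to trivial events. The protocol separates severity from seriousness. A reaction may be incapacitating or need medical intervention, and so be graded severe, without meeting the SAE definition. It then misses the 24-hour route unless someone judges it an important medical event.

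**Working it through.** **Which events reach the Monitor, and when**

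| Event | Required route to the Monitor | Timing |
|---|---|---|
| SAE | Report sent to her; written review | 24 hours |
| Death | Review required | No separate deadline in that sentence |
| Unanticipated problem | Review required | None stated |
| Anticipated, non-serious TheraGauze reaction | Chart review only | Every 3 to 6 months |

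Two routes could bring a non-serious-looking reaction forward, and both depend on judgment. An important medical event may be classed as serious. A reaction might also be called an unanticipated problem, but the protocol does not define that term, and Risks and Side Effects already lists a local allergic or irritation reaction to the packing. An ordinary local reaction would therefore not naturally qualify.

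**Size**

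The plan gives no figure to reproduce: it states no accrual rate, expected reaction rate or threshold. What follows is illustration.

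*Inputs.* 100 randomised at 2:1 (Study Size) gives 100 × 2/3 ≈ 67 TheraGauze subjects. Accrual of 12 to 36 months is my assumption. The wound-reaction rate is unknown. Background gives 3% irritation for tobramycin eye drops, and no side effects in 18 subjects using a wound ointment that also contained dexamethasone. The one-sided 95% upper bound for 0/18 is 1 − 0.05^(1/18) = 0.153. I use 3%, 10% (assumption) and 15% (that bound, not an expected rate).

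*TheraGauze subjects treated between two reviews.* 67/12 = 5.58 a month and 67/36 = 1.86 a month.
- 3-month gap: 5.58 × 3 = 16.75 down to 1.86 × 3 = 5.58, so 6 to 17.
- 6-month gap: 33.5 down to 11.17, so 11 to 34.

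*Expected reactions in one gap* (subjects × rate, from the shortest gap with slowest accrual to the longest gap with fastest): 0.2 to 1.0 at 3%; 0.6 to 3.4 at 10%; 0.8 to 5.0 at 15%.

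*Delay.* If reactions fall evenly between reviews, the mean wait is half the interval: 1.5 months or 3 months.

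*Load from prompt reporting over the whole trial* (67 × r): 2.0 at 3%, 6.7 at 10%, 10.0 at 15%.

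*Chance that a review at c cumulative reactions is ever called*, P(X ≥ c) with X ~ Binomial(67, r):

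| c | r = 3% | r = 10% |
|---|---|---|
| 2 | 0.601 | 0.993 |
| 3 | 0.326 | 0.969 |
| 4 | 0.142 | 0.913 |

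For c = 3 the chance is also 0.030 at 1%, 0.657 at 5%, 0.912 at 8% and 0.998 at 15%. The median number treated at the third reaction is 27 at 10% and 18 at 15%. With a review at every third reaction, the expected number of reviews, E[floor(X/3)], is 0.34, 1.90 and 3.02 at 3%, 10% and 15%.

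*Incomplete detection.* Study Size expects only half of subjects to complete. At a true 10% rate with c = 3, the chance is 0.969 if every reaction is detected, 0.887 if 75% are (counted rate 7.5%) and 0.657 if half are (counted rate 5%).

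**The case against.** The strongest reply is that this is deliberate tiering: serious events at once, the rest at periodic review, under a Monitor with full power to stop. Much of that stands. The plan contains no contradiction, and nothing bars the PI from telling the Monitor sooner. She may talk to investigators and interview subjects at any time. The Amendments section exempts changes needed for subject safety from prior IRB approval, so action need not wait for her. The packing is placed once, comes out around Day 3, and is removed at once if a reaction occurs. None of this, however, requires that she be told. The Research Monitor section also has related events forwarded promptly to the Army human research protection office. In context that sentence may cover only SAEs, unanticipated problems and deaths, and in any case it sends reports outward, not to her.

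The following stronger readings are tempting, but the documents do not support them:

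- *The trial has no trial-level stopping provision.* It has one, held at the Monitor's discretion. What is absent is a stated trigger.
- *Local reactions go unseen.* The PI judges causality and severity for every AE and does most Visit 3 assessments.
- *No non-serious event can reach the Monitor early.* An unanticipated problem must be reviewed whether or not it is serious.
- *The subjects treated between reviews are exposures that faster reporting would avert.* They are not. An earlier look prevents exposure only if the Monitor then chooses to pause, and near a 3% rate there would be little to act on.

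The number 3 is also arbitrary, and a count in one arm does not separate infection from toxicity. For these reasons it should prompt a review and not a stop.

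**Conclusion.** The point holds in a narrow form and is minor. For anticipated, non-serious TheraGauze reactions, including severe ones, the only required route to the Monitor is the 3-to-6-month chart review, and the Stopping Rules govern one subject at a time. The consequence is delayed independent review, on average 1.5 to 3 months if reactions are evenly spread. The reading of the text needs no assumption. The sizes depend on assumed accrual and on reaction rates not known for this product in wounds. If the true rate is near 3% the gain is small; near 10% or above, a cluster would probably form and earlier joint review would be more useful. The change is worth making because it is cheap and safety is the primary endpoint, not because the present oversight is unsound.

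**What to change.** Keep the packing-removal rule. Add to Stopping Rules:

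1. Each investigator-assessed TheraGauze adverse reaction, serious or not, is sent to the existing Research Monitor within about 2 working days, with the running count over TheraGauze subjects treated. The 24-hour rule for SAEs is unchanged.
2. When the count reaches a small number agreed in advance by the sponsor and the Monitor (for example 3, and each further multiple), she reviews the cases together, against control-arm events where relevant, and records whether enrolment continues or pauses.

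No new committee or automatic pause is needed.

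The cost is one or two sentences and existing staff time: about 2 extra reports over the trial at 3%, or 7 at 10%. The downside is an occasional unneeded review. With 3 as the number, the chance of at least one review is 33% at a counted 3%, rising to 91% at a counted 8%, for example if infection-related pain or redness is counted as a reaction. Applying the protocol's existing distinction between progression of infection and local toxicity before counting would limit this.
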